Clinical study protocol

Project name: Comparison of traditional regression model and AI in predicting prolonged ICU stay after head and neck tumors

Sponsor: Sun Yat-sen Memorial Hospital of Sun Yat-sen University

Version number: V1.0

Version date: 2024.3.21

Project leader: [name]

Scheme signature confirmation: TBEV

-, Abstract of the study protocol

Title: Comparison of traditional regression model and AI to predict prolonged ICU stay after head and neck tumors

Brief description of the study: This experiment is a cohort observational study. By establishing a cohort of patients with head and neck tumors after surgery, we compared the prediction effect of AI and traditional prediction models on whether patients with ICU can be transferred to ICU within 24 hours after head and neck tumors after surgery. First, retrospective analysis of postoperative patients with head and neck tumors, patients' medical records were collected, and the patients were divided into training group and validation group according to 7:3, divided into 2 groups according to whether the ICU stay time was greater than 24 hours, and the prediction model of postoperative ICU stay time of head and neck tumors over 24 hours was established after using LASSO regression to select variables. At the same time, the data was cleaned, the AI was trained, and the efficacy was compared by ROC. After the establishment of prediction model and AI training, the patients included in the cohort were evaluated by prediction model and AI evaluation immediately after transfer to the ICU, which predicted the possibility of transferring out of the ICU within 24 hours.

Study jects: All patients with head and neck tumors

Outcome measures: The patient was transferred out of the ICU Sample size: Following the principle of 10 times the sample size, the included sample size is more than 10 times of the final variable, and 500 patients are currently expected to be included.

2. Research background (including the introduction of the disease, the treatment status at home and abroad, the significance of the research, etc.)

Head and neck tumor incidence ranks the sixth [1] in the global tumor incidence.

The incidence of head and neck tumors is increasing in China and is expected to reach 3.99 [2] per 100,000 people by 2049. Surgical resection has been identified as the primary treatment for oral cancer [3]. Because of the complex anatomy of the oral region, limited surgical space, and the need for simultaneous flap reconstruction to protect the integrity of the oral and maxillofacial systems, about 80% of patients undergoing oral cancer surgery will be transferred to the intensive care unit (ICU) after the operation, [4].

Previous studies found that prolonged ICU stay was associated with poorer prognosis and quality of life, causing a substantial disease and economic burden of [4]. ICU stay> 24 h implies a higher risk of nosocomial infection [5-7] and worsen the prognosis [8] in oral cancer patients. Previous studies found that ICU admission delayed oral feeding time and negatively correlated with 5-year survival [8,9]. Therefore, it is important to identify oral cancer patients with a long ICU after surgery.

Most patients with head and neck tumors have postoperative ICU stay time between 24 and 72 hours [10-12]. In a retrospective study of the UK National Intensive Care database, the median stay of patients undergoing head and neck cancer surgery was found in the ICU of 24 hours (IQR 18.8-46 hours) [13]. Meanwhile, according to our clinical experience, we believe that the ICU stay time of postoperative head and neck tumor patients should be within 24 hours is reasonable.

Currently, the study of ICU stay time after head and neck cancer surgery has focused on demographic characteristics, surgical methods, blood transfusion and physiological scores of [8,9,14]. Previous studies have evaluated some risk factors associated with prolonged length of stay (LOS). Poor nutritional status and unhealthy lifestyle habits are associated with prolonged ICU stay in [15,16]. Furthermore, surgery-related factors such as intraoperative blood transfusion and flap reconstruction methods were [5,17] associated with LOS in patients undergoing surgery for head and neck tumours. However, there are few studies on the effect of laboratory results on ICU stay time after head and neck cancer surgery. Consideration of laboratory findings as potential predictors of ICU stay is warranted. These measurements include liver and renal function indicators, electrolyte levels and lactate levels, etc. Developing a predictive model for identifying patients with a prolonged ICU stay (> 24 hours) after head and neck cancer surgery is of great clinical importance. We plan to use the patient's clinical data to build a prediction model and AI prediction model to predict whether the head and neck tumor can be transferred out of the ICU within 24 hours after surgery, compare the efficacy of AI with the traditional prediction model, and subsequently validate his efficacy in a prospective cohort.

Head and neck tumor incidence ranks the sixth [1] in the global tumor incidence. The incidence of head and neck tumors is increasing in China and is expected to reach 3.99 [2] per 100,000 people by 2049. Surgical resection has been identified as the primary treatment for oral cancer [3]. Because of the complex anatomy of the oral region, limited surgical space, and the need for simultaneous flap reconstruction to protect the integrity of the oral and maxillofacial systems, about 80% of patients undergoing oral cancer surgery will be transferred to the intensive care unit (ICU) after the operation, [4].

Previous studies found that prolonged ICU stay was associated with poorer prognosis and quality of life, causing a substantial disease and economic burden of [4]. ICU stay> 24 h implies a higher risk of nosocomial infection [5-7] and worsen the prognosis [8] in oral cancer patients. Previous studies found that ICU admission delayed oral feeding time and negatively correlated with 5-year survival [8,9]. Therefore, it is important to identify oral cancer patients with a long ICU after surgery.

Most patients with head and neck tumors have postoperative ICU stay time between 24 and 72 hours [10-12]. In a retrospective study of the UK National Intensive Care database, the median stay of patients undergoing head and neck cancer surgery was found in the ICU of 24 hours (IQR 18.8-46 hours) [13]. Meanwhile, according to our clinical experience, we believe that the ICU stay time of postoperative head and neck tumor patients should be within 24 hours is reasonable.

Currently, the study of ICU stay time after head and neck cancer surgery has focused on demographic characteristics, surgical methods, blood transfusion and physiological scores of [8,9,14]. Previous studies have evaluated some risk factors associated with prolonged length of stay (LOS). Poor nutritional status and unhealthy lifestyle habits are associated with prolonged ICU stay in [15,16]. Furthermore, surgery-related factors such as intraoperative blood transfusion and flap reconstruction methods were [5,17] associated with LOS in patients undergoing surgery for head and neck tumours.

However, there are few studies on the effect of laboratory results on ICU stay time after head and neck cancer surgery. Consideration of laboratory findings as potential predictors of ICU stay is warranted. These measurements include liver and renal function indicators, electrolyte levels and lactate levels, etc. Developing a predictive model for identifying patients with a prolonged ICU stay (> 24 hours) after head and neck cancer surgery is of great clinical importance. We plan to use the patient's clinical data to build a prediction model and AI prediction model to predict whether the head and neck tumor can be transferred out of the ICU within 24 hours after surgery, compare the efficacy of AI with the traditional prediction model, and subsequently validate his efficacy in a prospective cohort.

3. Study objective (clear objective)

3.1.1 Main Purpose

Comparing the prediction accuracy of AI and traditional prediction models for ICU stay time after head and neck tumors.

3.1.2 Secondary Purpose

Explore the construction method and influencing factors of ICU stay time prediction model after head and neck cancer surgery.

4. research design

This study is a cohort observational study by establishing a retrospective cohort of patients transferred to ICU for head and neck tumors from January 2022 to December 2023, which is exempt from informed consent. Screen the variables to establish the traditional prediction model and train the AI, and then compare the accuracy of the traditional prediction model and the AI. After the validation on the basis of retrospective study of the traditional model and the prediction of AI for head and neck tumor patients postoperative ICU stay time, prospectively into the head and neck tumor postoperative ICU patients, the patient in the ICU to sign the waste specimen use consent, through prospective studies to verify the AI in ICU stay time prediction superiority.

5. Research protocol and technical route (including the calculation of study sample size, inclusion, exclusion, withdrawal criteria, evaluation indicators and methods of study results, statistical analysis plan, informed consent, ethics, etc.)

Sample size: Following the principle of 10 times the sample size, the included sample size is more than 10 times of the final variable. Currently, 500 retrospective patients and 200 prospective patients are expected to be included.

Selection criteria

Patients after head and neck tumors, older than 18 years.

Exclusion criteria

1 Patients transferred to ICU twice after head and neck tumors

2. Patients with unplanned transfer to the ICU

Evaluation indicators and methods of the results: compare the effectiveness of the model using accuracy or ROC

Statistical analysis plan: data description of statistical analysis, analysis methods of primary / secondary indicators / safety indicators, statistical school positive methods, control of bias, stratification / subgroup / sensitivity analysis, etc

All data were statistically analyzed using SPSS 25.0 and R languages, and P <0.05 was considered statistically significant.

The measurement data conforming to the normal distribution are described by the mean standard deviation \pm (x \pm s); the measurement data that do not conform to the normal distribution are described by the median (M) and interquartile spacing (P25-P75); the counting data are described by frequency and percentage (%); the lacking measurement data are filled by mean, and the missing counting data is filled by mean.

Comparison of differences between groups: t-test was used for the measurement data meeting the normal distribution, rank sum test for the measurement data, \times 2 test, Fisher exact probability method or continuous corrected chi-square test for the counting data.

Informed consent: Exemption from informed consent for retrospective part. Signed informed consent for transfer to ICU.

VI. Safety evaluation (including the definition and assessment of adverse events and serious adverse events)

There is no direct interventional operation in this study, and the risks mainly include possible errors in data collection and management, as well as patient privacy protection issues.

Vii. Data collection and management

All data are retrieved and cleaned after export from the big data system. All data are retrieved by the database software. The relevant data are as

follows:

Baseline data:

Patients collected from the electronic medical records of admission baseline data: age, gender, Body Mass Index, body mass index (BMI), past history [including oral cancer treatment (radiotherapy, chemotherapy, immunotherapy), previous basic disease history (hypertension, diabetes history)], personal history (including smoking history, drinking history), family history of oral cancer, tumor site; Pre-operative indicators:

(1) Clinical Assessment Scale: Nutritional Risk Screening Scale (Nutritional Risk Screening-2002, NRS-2002) (see Supplementary Table 1); (2) Preoperative laboratory examination results: blood routine [white blood cell count $(10^9/$ L), hemoglobin (g / L), platelets $(10^9/$ L), neutrophil count $(10^9/$ L), lymphocyte count $(10^9/$ L), monocyte cell count $(10^9/$ L), red blood cell volume (fL), the ratio of neutrophil count to lymphocyte count (Neutrophil-to-Lymphocyte Ratio, NLR), the ratio of lymphocyte count to monocyte count (Lymphocyte-to-Monocyte Ratio, LMR)], Coagulation function [plasma prothrombin time (s), fibrinogen (g / L), activated partial thromboplastin time (s), thrombin time (s), D-dimer (mg/L)], Liver function [glutamate aminotransferase (U / L), glutamate aminotransferase (U / L), albumin (g / L)), Renal function (creatinine (u mol/L)], Blood electrolytes [potassium ion (mmol/L), sodium ion (mmol/L), calcium ion (mmol/L), chloride ion (mmol/L)];

Procedure-related indicators:

Operation duration (h), flap type (none, fibula, femur, pectoralis major), scope of cervical lymph node dissection (none, unilateral, bilateral); Index of postoperative monitoring:

(1) Clinical assessment scale: Acute Physiological and Chronic Health Assessment II score (Acute Physiology and Chronic Health Evaluation II, APACHE II), Sequential Organ failure score (Sequential Organ Failure Assessment, SOFA), Caprini venous thrombosis risk score; (2) Related indicators of ICU monitoring: time of mechanical ventilation, body temperature [mean body temperature in the first 24h after transfer to ICU (°C), highest body temperature (°C) in the first 24h after transfer to ICU, minimum body temperature $(^{\circ}C)$], arterial pressure [mean arterial pressure (mmHg) in the first 24h after transfer to ICU, highest mean arterial pressure (mmHg) in the first 24h after transfer to ICU, lowest mean arterial pressure (mmHg) in the first 24h after transfer to ICU]; ③ First postoperative laboratory examination: blood routine [white blood cell count $(10^{9}/$ L), hemoglobin (g / L), platelets $(10^{9}/$ L), neutrophil count $(10^{\circ}/L)$, lymphocyte count $(10^{\circ}/L)$, monocyte cell count $(10^{9}/$ L), red blood cell volume (fL), NLR, LMR], Coagulation function [plasma prothrombin time (s), fibrinogen (g / L), activated partial thromboplastin time (s), thrombin time (s), D-dimer (mg/L)], Liver aminotransferase (U / L), function [glutamate glutamate transaminotransferase (U / L), albumin (g / L)], Renal function [creatinine (u mol/L)), Blood electrolytes (potassium ion (mmol/L), sodium ion (mmol/L), calcium ion (mmol/L), chloride ion (mmol/L)]; Blood gas analysis [pH, partial pressure of carbon dioxide (kPa), partial pressure of oxygen (kPa), lactic acid (mmol/L)].

八、 Quality management plan (please introduce relevant measures to ensure project quality and progress)

Data processing by special person, in addition, data review by special personnel to determine the authenticity of the data, each data processing steps are retained to ensure the repeatability of the experiment.

IX. Pre-assessment and risk control plan of project risk benefits (Please describe the risks and benefits of the researchers, subjects and the medical institution; if there are risks, please introduce the measures and feasibility of risk control.)

By comparing the ICU stay time of head and neck cancer, it is expected

to improve the efficiency of postoperative management of head and neck cancer patients and reduce the waste of medical resources.

X. References

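### The 10-patients-per-variable rule fixes neither the 500 nor the 200, and seven listed data items are not known at the stated time of prediction

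*Protocol*

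**What the plan says.** - **Size.** Section 5 (Research protocol and technical route), whose heading says it includes the sample-size calculation, states: "the included sample size is more than 10 times of the final variable. Currently, 500 retrospective patients and 200 prospective patients". The abstract repeats the rule but says only that "500 patients are currently expected to be included".
- **Development.** In the abstract, "the patients were divided into training group and validation group according to 7:3", and the regression model "was established after using LASSO regression to select variables". The number of final variables is therefore unknown until the selection has run.
- **Use.** In the abstract, patients in the cohort "were evaluated by prediction model and AI evaluation immediately after transfer to the ICU". The outcome is an ICU stay of more than 24 hours.
- **Purpose of the prospective part.** Section 4 (research design): "through prospective studies to verify the AI in ICU stay time prediction superiority".
- **Measure.** Section 5: "compare the effectiveness of the model using accuracy or ROC".
- **Data.** Section VII (Data collection and management) lists the relevant data. Under postoperative monitoring these include time of mechanical ventilation, three body-temperature summaries and three arterial-pressure summaries. Five of these six are labelled as covering the first 24 hours after transfer. The minimum temperature stands in the same bracket without its own label.

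**The concern.** The main purpose (section 3.1.1) is to compare the accuracy of AI and regression. As planned, that comparison rests on 150 hold-out patients and then 200 prospective patients. The one rule given concerns how many variables a fitted model may carry. It contains no term for a difference between two models, so it cannot justify a sample meant to show that one is better.

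The timing problem matters more for validity. If either model keeps one of the seven monitoring items, there are two possibilities. Either the prospective prediction cannot be made at the stated time, or it is made later with data from the same 24 hours that decide the outcome. In the second case the measured performance is not that of a prediction on arrival.

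**Working it through.** **1. What the rule yields.** N > 10k, with k the number of final variables.
- N = 500: k < 50, so k up to 49.
- Training set 0.7 x 500 = 350: k < 35, so k up to 34.
- In reverse, k = 10 requires more than 100 patients, k = 20 more than 200 and k = 30 more than 300. The rule returns about 500 only if k is about 49-50, a number the protocol does not give.

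There is thus no calculation to reproduce. The 500 satisfies the rule for any k up to 49 but does not follow from it.

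**2. Items listed in section VII.**

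| Block | Items |
|---|---|
| Baseline | 12 |
| Preoperative: NRS-2002 1, blood routine 9, coagulation 5, liver 3, renal 1, electrolytes 4 | 23 |
| Procedure | 3 |
| Postoperative: scores 3, ventilation time 1, temperature 3, arterial pressure 3, laboratory 22, blood gas 4 | 36 |
| Total | 74 |

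Coding flap type (4 levels) adds 2 parameters and neck dissection (3 levels) adds 1, giving at least 77; tumour-site levels are not stated. Removing the seven monitoring items leaves 67 items and at least 70 parameters. These counts apply only if every listed item is offered to the selection.

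**3. Patients in the smaller outcome class per parameter.** The background section reports that "the median stay of patients undergoing head and neck cancer surgery was found in the ICU of 24 hours", which suggests about 50% prolonged. The same section says most patients stay 24 to 72 hours, so a smaller class below 50% is plausible; 25% is my assumption.
- 350 patients, 77 parameters: 175/77 = 2.3 at 50%; 87.5/77 = 1.1 at 25%.
- 500 patients, 70 parameters: 250/70 = 3.6 at 50%; 125/70 = 1.8 at 25%.

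**4. Precision, taking AUC as the measure.** Hanley-McNeil variance, with n1 prolonged and n0 not prolonged:

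Var(A) = [A(1-A) + (n1-1)(Q1-A²) + (n0-1)(Q2-A²)] / (n1 n0), where Q1 = A/(2-A) and Q2 = 2A²/(1+A).

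For the 150 hold-out patients, the standard error of one AUC is 0.036 (A = 0.80, classes equal) to 0.050 (A = 0.75, 25% prolonged).

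For the 200, the SE of the paired difference is √(v1 + v2 - 2r√(v1 v2)), where v1 and v2 are the two variances and r is the between-model correlation. The detectable difference at two-sided 5% and 80% power solves d = (1.960 + 0.842) x SE.

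Example: 100 per class, AUC 0.80 against 0.853, r = 0.8. Then v1 = 0.000984 and v2 = 0.000743, so SE = √(0.001727 - 0.001368) = 0.0189 and d = 2.802 x 0.0189 = 0.053.

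| r | Detectable difference (lower AUC 0.75-0.80, smaller class 25-50%) |
|---|---|
| 0.9 | 0.038-0.053 |
| 0.8 | 0.053-0.073 |
| 0.5 | 0.080-0.111 |

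If the patients who are not prolonged form the 25% class, the results fall inside these ranges. A simulation of a LASSO-selected regression and a small neural network, with every setting assumed, gave correlations of 0.87-0.91 between the two hold-out AUC errors. The first row should therefore not be left out.

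**5. Timing, side by side.** The abstract fixes prediction at arrival in the ICU. A mean, maximum or minimum over the first 24 hours is complete only when those hours are over, and ventilation time only when ventilation ends. The outcome is settled at the same 24-hour mark. The two passages are compatible only if these seven items stay out of both models, and the protocol does not say so.

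**The case against.** - **The 500 may never have been meant as a calculated figure.** The retrospective cohort is a fixed window, January 2022 to December 2023, and 500 is described as expected. It can be read as a head count checked against a floor. That is fair, and it is the better way to state it. It does not help the 200, in whom the floor has nothing to check.
- **A reader might infer that 500 or 200 is too few.** The protocol does not support that. The 500 does not breach the stated rule for any model of up to 49 variables. Whether 200 suffices depends on a target difference and a correlation that are not given.
- **Section VII is a collection list, not a candidate list.** This stands. The items may serve the secondary purpose of exploring influencing factors, and a statistical analysis plan that is not shown may name the candidates. So 77 and 70 are conditional figures, and the timing conflict bites only if one of the seven items is kept. But the protocol names no narrower list.
- **A reader might also infer that the 7:3 split is an error.** It is not. A hold-out is valid, only less efficient. In the simulation the root mean square error of the AUC difference was 0.0170-0.0271 with the hold-out and 0.0136-0.0210 with cross-validation on all 500. The gain is modest and rests on assumed settings, and the protocol does not specify its AI method.

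**Conclusion.** The concern holds in a limited form. The rule is a floor that does not determine 500 and is irrelevant to a superiority check in 200; this follows from the text and simple arithmetic. The mismatch between 500 in the abstract and 500 + 200 in section 5 is also plain. The timing conflict is internal to the protocol and is the part most likely to distort the result, on the condition that a model keeps one of the seven items. The direction of any resulting bias between AI and regression is unknown, so it cannot be said to favour either.

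The detectable differences in the 200 span about 0.04 to 0.11. They rest on assumed AUCs, class balance and correlation, and on AUC rather than accuracy being the measure. They describe what 200 patients can show; they do not prove the number wrong.

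**What to change.** No additional patients are needed.

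1. Restrict the candidates of both models to values available at the stated prediction time. This excludes ventilation time and the six temperature and pressure summaries. Confirm that the 26 first postoperative laboratory and blood gas results and the three postoperative scores are available then, and exclude any that are not.
2. Stop presenting the 10-times rule as the basis for either number. State 500 as the count expected from the January 2022 to December 2023 window. Give the number of candidate parameters actually entered and the smaller-class patients per parameter. If all items but the seven enter, that is at least 70 parameters, with 3.6 patients each at 50% prolonged stay and 1.8 if the smaller class is 25% (an assumption).
3. For the 200, report the paired AUC difference with a 95% confidence interval. State the detectable differences by correlation (about 0.04-0.05 at 0.9, 0.05-0.07 at 0.8, 0.08-0.11 at 0.5) with their assumptions, and soften the wording about verifying superiority accordingly.
4. Give 500 + 200 in the abstract.
5. Optional, as an improvement and not a correction: develop both models on all 500, with repeated cross-validation or bootstrap that repeats imputation, selection and tuning on the same resamples for both. Keep the 200 untouched for validation.

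**Cost.** Items 1 to 4 are mainly wording and an availability check. Dropping the seven items may lower the retrospective AUC, the stated ratio will look less favourable than 10 to 1, and the superiority claim becomes weaker. Item 5 changes the retrospective validation design: it takes more computing and loses the simple hold-out figure. Its estimates are also slightly pessimistic (AUC 0.007-0.015 too low in the simulation).

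### Exclusion 1, as worded, drops a whole patient for a second ICU transfer that can only happen after the prediction and its outcome; the index stay needs defining

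*Protocol*

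**What the plan says.** The protocol's section 5 has one list of criteria for the whole study. The first exclusion reads "Patients transferred to ICU twice after head and neck tumors" and the second "Patients with unplanned transfer to the ICU". Neither names an index operation, an index ICU stay or a time window. The same section plans for both cohorts together: "500 retrospective patients and 200 prospective patients are expected to be included".

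The other relevant statements are these:

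- **Timing of the prediction (abstract, brief description).** After model building, cohort patients are to be "evaluated by prediction model and AI evaluation immediately after transfer to the ICU".
- **Outcome (abstract, brief description).** Patients are "divided into 2 groups according to whether the ICU stay time was greater than 24 hours". The text does not say which stay is meant if there is more than one.
- **Prospective entry (section 4).** The design has "the patient in the ICU to sign the waste specimen use consent".
- **Subjects (abstract).** They are given as "All patients with head and neck tumors".
- **Evaluation (section 5).** The plan is to "compare the effectiveness of the model using accuracy or ROC".

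**The concern.** An entry criterion should be decidable when the patient enters, and for a prediction study that means no later than the prediction. Exclusion 1, read as written, depends on something that happens afterwards. In the prospective cohort it would take out patients who had consented, been scored by both models and reached their 24-hour outcome. In the retrospective cohort it can be applied with hindsight, but the training and validation sets are then selected on a later event.

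What is at stake is whom the results describe. The models are meant for use on arrival, when nobody knows who will come back. Performance measured only in patients who did not come back is performance in a group that cannot be picked out at the time of use. Patients who left the ICU and returned are also relevant to a model about leaving within 24 hours, and the rule takes them out of view.

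Because there is no time limit, the chance of being excluded also depends on how long each record is observed. A patient admitted in January 2022 has had longer to show a second transfer than one admitted in December 2023 or one recently enrolled prospectively. The same sentence can therefore select the two cohorts differently. It would also drop a patient who had two separate operations, each followed by a planned ICU stay.

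**Working it through.** **Order of events.** No stated figure needs reproducing, because the point rests on time order. For a patient entered on a first ICU stay:

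1. The patient arrives in the ICU. In the prospective cohort, consent is signed in the ICU (section 4) and both models are applied at once on transfer (abstract).
2. The 24-hour mark passes, or the patient leaves before it. The outcome of this stay is settled no later than the end of the stay.
3. The patient leaves the ICU.
4. Only now can a second transfer occur, and only then does exclusion 1 become true.

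Exclusion 1 is therefore undecided at steps 1 to 3. Exclusion 2 does not resolve this: it concerns whether a transfer was planned and does not say which transfer is analysed. If it too is read by patient, an unplanned return would also remove the first stay.

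**Possible size.** The protocol gives no rate of return to the ICU, so the rates below are assumptions.

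*Inputs.* n = 500 and n = 200 are the planned included numbers (section 5), that is, counts after exclusions. The return rate r is assumed to be 2–5%. The gap in accuracy between retained and returning patients is assumed to be 10–30 percentage points.

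*Patients removed to reach n included* = n·r/(1−r); *number before this exclusion* = n/(1−r).

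| n included | r | removed | before exclusion |
|---|---|---|---|
| 500 | 2% | 500×0.02/0.98 = 10.2 | 510.2 |
| 500 | 5% | 500×0.05/0.95 = 26.3 | 526.3 |
| 200 | 2% | 200×0.02/0.98 = 4.1 | 204.1 |
| 200 | 5% | 200×0.05/0.95 = 10.5 | 210.5 |

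*Shift in overall accuracy.* Accuracy in all arrivals is (1−r)·(accuracy in retained) + r·(accuracy in returning). Accuracy in the retained patients therefore differs from it by r × gap:

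- r = 2%: 0.02×10 = 0.2 to 0.02×30 = 0.6 points
- r = 5%: 0.05×10 = 0.5 to 0.05×30 = 1.5 points

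The sign depends on whether returning patients are harder or easier to predict, which the protocol cannot tell us.

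*Shift in the share staying over 24 hours.* With p the share in all first stays and q the share in first stays of returning patients, the share after exclusion is (p − r·q)/(1−r). Taking p = 50% and q between 20% and 80%, both assumed, r = 5% gives (0.50−0.05×0.8)/0.95 = 48.4% to (0.50−0.05×0.2)/0.95 = 51.6%.

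*For scale.* At an assumed accuracy of 80% with 200 patients, the 95% half-width is 1.96×√(0.8×0.2/200) = 5.5 points.

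**The case against.** The strongest reply is that the line is a translation and is probably an ordinary screening rule: on arrival, staff check whether the patient has already been in the ICU after this operation, and a second arrival is not enrolled. Exclusion 2 is also known on arrival, which supports reading both lines as describing the arriving transfer. No other passage orders the removal of a patient already scored. On this reading nothing is selected on a later event, and the first stay is the index stay by default. On the literal reading every retained patient has one ICU stay, so the 24-hour label is clear without further definition. Either way, both models are scored on the same patients, so the main purpose, comparing AI with regression, is not visibly harmed. The abstract's broad description of subjects is a label that eligibility criteria normally narrow.

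Much of this stands. The benign reading is possible, the label on the first stay is correct, no bias in the comparison can be shown, and the illustrative shifts lie well inside the sampling error of 200 patients. Narrowing a broad label is not in itself a contradiction.

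It does not remove the point. The protocol nowhere states the benign reading. A retrospective extraction has no moment of arrival at which to turn anyone away: the record shows both transfers, and the sentence as written tells the data team to drop the patient. Two teams could build different cohorts from the same line. The difficulty with the narrowing is its kind: age and planned transfer are known on arrival, whereas a future return is not.

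**Conclusion.** The concern holds as stated. Followed as worded, exclusion 1 selects the training, validation and prospective sets on an event after the prediction, and leaves a study population that cannot be identified when the models are used. That conclusion rests on the text and the order of events alone.

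The size is unknown and probably small. The illustrative 0.2–1.5 points of overall accuracy, in either direction, depend entirely on the assumed return rate and accuracy gap. Neither the direction nor the size of any effect on accuracy, AUC or the AI-versus-regression comparison can be derived from the protocol. The point concerns whom the results apply to. It should be corrected, but it does not undermine the comparison. Confidence is medium, because the sponsor may have meant only to turn away repeat arrivals.

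**What to change.** Replace exclusion 1 with a definition such as: *the index stay is the first planned postoperative ICU stay; later ICU stays are not separate index stays and do not remove the patient.* Score the 24-hour outcome on that stay, word exclusion 2 as referring to the index transfer, and apply the same rule in both cohorts. This wording works whichever meaning was intended. Optionally, report descriptively how many patients returned, split by transfer out within or after 24 hours.

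The cost is an amendment to two lines. If returning patients have already been left out of the 2022–2023 extract, their records must be pulled from the same hospital system and cleaned, roughly 10–26 at the assumed rates. The analysis will also keep a few patients who may be harder to predict. The change is easiest before the retrospective data are fixed and prospective enrolment begins.
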